Recently, Drs. [name] and [name] conducted a feasibility open trial of BCBT in adult inpatients. Their findings suggest that BCBT may be a helpful intervention for adults hospitalized following a suicide attempt. Also recently, Sinyor et al. (2020) examined BCBT in youth hospitalized after an episode of suicidal behavior and despite small numbers, found a significant reduction in suicide behavior in the BCBT group. It is essential to examine whether this approach yields similar reductions in suicide re-attempt risk among adolescents, as well as whether this intervention can be delivered effectively via a smartphone app. We aim to build on their promising findings and extend this line of research to adolescent inpatients by developing a youth adapted version of our smartphone app product A [REDACTED] We will collect pilot feasibility data on [REDACTED] from this new population.

Specific Aim 1 – Create a beta version of [REDACTED] for youth (ages 13 - 17). Drawing on our experience in developing and implementing digital applications (i.e. "mobile apps" for Apple/Android devices) that have been shown to increase access to effective care for a variety of conditions (e.g. insomnia, anxiety, substance use) and are now available in benefit packages for over 50 million covered lives nationally, we will prepare the release of a beta version of A [REDACTED]. Creation of this beta version will constitute the bulk of the work to be accomplished in our proposed twelve-month Phase I project. [REDACTED]

Specific Aim 2 – To test the feasibility and acceptability of the beta version of [REDACTED] in a single-group, open-label trial. Following its creation, we will test the feasibility and acceptability of the Beta Version of [REDACTED] in a clinical sample of 20 adolescents (ages 13 - 17) who were recently admitted for suicidal ideation with a suicidal plan or report a lifetime suicide attempt. This will be done in a single-site, 16-week, single-group clinical trial. Feasibility and acceptability will be measured with logs and questionnaires.

Anticipated Outcome and Future Directions: [REDACTED]

BACKGROUND AND SIGNIFICANCE

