B.2.5. Secondary Endpoints. Diagnostic interviews will be conducted with each participant with the **Mini International Neuropsychiatric Interview Neurocognitive for Children and Adolescents (MINI-KID)**, a widely used, structured diagnostic interview that will be used to verify diagnosis at the screening visit (Sheehan et al 2010). Secondary endpoints will consist of the following measures, assessed using a within-group comparison, over time: **1) Suicidal ideation.** The Suicide Ideation Questionnaire (SIQ) is a 30 – item self or clinician administered instrument used to measure the current intensity of patients' specific distress and suicidal intent, which has been validated for use with adolescents (Pinto et al 1997). Score range is 0-180, with higher score indicating higher intensity. **2) Suicide attempts and other behaviors.** This outcome will be assessed via the Columbia Suicide Severity Rating Scale (CSSRS), which was designed to classify suicide attempts, aborted suicide attempts, and other suicidal behaviors and has been validated for use with adolescents (Gipson et al 2015). **3) Depressive symptoms.** The Patient Health Questionnaire (PHQ-9) is a 9-item self-report form to assess the severity of depressive symptoms that has been widely used in practice and research and validated for use with adolescents. This will be used throughout the study to assess severity of any depressive symptoms each subject is experiencing (Richardson et al 2010).

B.2.6. Participant Remuneration for follow-up sessions. All participants will be paid \$20 for completing each post-discharge assessment (weeks 1, 4, 8, 12, and 16; \$100 total) and a \$25 bonus for completing all assessments. Adolescents and parents/guardians will be paid separately, with separate ClinCards, for their participation (maximum \$125 each). Data from parent/guardians will continue to be collected in cases where participants reach age of maturity during study participation so long as the child continues participation in the study as an adult (i.e., signs adult informed consent form). Parent/guardian date of birth is required in order to register the ClinCards to the parent/guardian. This information will be collected during the consenting process. Payments will not be prorated for partial completion of assessments. Sufficient funding has been budgeted for this portion of the project (see Budget Justification).

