B.2.11. Rationale for Number of Subjects. We will recruit 20 youth age 13-17 years who complete enrollment in the [REDACTED] app. Expecting 10% attrition rate before completing enrollment in the [REDACTED] app we will consent 22 youths to reach our target enrollment number of 20. Means, medians, ranges, and standard deviations for the length of time taken for patients to work through the intervention and for patients to complete the eligibility interview, baseline, post-treatment (8 weeks) and follow-up (12 and 16 weeks) assessments will be reported. In addition, means and SDs will be reported for the length of time it takes project personnel to administer the data collection procedures from invitation through treatment. These data will be used to assess the feasibility of the intervention and study procedures. They will also be used for formal power calculations to design an adequately powered RCT in a subsequent project.

TIMELINE

	Screening Period ^{a, f}	App Testing Period					Follow-Up Period	
Week(W)	W0	W1 ^b	W1-3	W4 ^b	W5-7	W8 ^b	W12 ^b	W16 ^b
Informed Consent	X							
Participant Information Sheet ^c	X							
Medications at Discharge (from medical record)	X							
Medication history form (parent report)		X		X			X	X
Research team phone call with outpatient provider		X						
Enrollment in [REDACTED]	X							
Mini-international neuropsychiatric interview (MINI-KID)	X							

Health Screen Interview	X							
Suicide Ideation Questionnaire (SIQ)	X	X		X		X	X	X
AE Assessment)	X	X		X		X	X	X
Patient Health Questionnaire (PHQ-9)	X	X		X		X	X	X
Columbia Suicide Severity Rating Scale (C-SSRS) - lifetime	X							
Columbia Suicide Severity Rating Scale (C-SSRS) – since last contact		X		X		X	X	X
Frequency of Use of App ^d		X	X	X	X	X	X	X
Interviews for feedback [REDACTED]		X		X		X	X	X
Utility of Techniques		X		X		X	X	X
Usability and Acceptability ^e		X		X		X	X	X
Assessment of healthcare resource utilization (parent report)		X		X		X	X	X

a Screening will be conducted while adolescent patients are at an inpatient psychiatric facility.

b Over the phone with member of the research team

c Sheet to collect demographic and contact information

d Unique logins and duration of each login

e System Usability Scale

f Visit 0 may take place over multiple sessions

RECRUITMENT AND RETENTION PLAN

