Risk Management. Suicidal ideation/behaviors will be assessed during each study interview (Week 0, Week 1, Week 4, Week 8, Week 16). Week 0 is the study baseline assessment, which occurs while the participant is housed in an inpatient treatment facility. For purposes of risk management, results of the study assessment at Week 0 will be shared with the inpatient treatment team in order to provide information relevant to their treatment/discharge planning. Remaining assessments are conducted by phone. In order to facilitate risk management during these calls we will do the following: 1) only enroll participants who provide assent/consent for the study to release information to their parent/guardian (note a parent/guardian interview is also routinely completed at this time), 2) only enroll participants who provide assent/consent for the study to release information to their outpatient provider (note that provider information may not be known at the time of consent in which case authorization will be obtained at the earliest possible time after provider information is known prior to making the initial outpatient provider call), 3) obtain location information at the start of each phone assessment, and 4) schedule phone assessments at a time when the parent/guardian is present at the same location as the participant. In addition to the routine outpatient provider call at week 1, increases in suicide risk will be communicated to the parent/guardian and outpatient provider. Details of study assessments indicating changes (i.e., increases) in risk since the previous assessment will be shared with the parent/guardian and outpatient provider. In addition, interviewers will engage in risk management interventions as clinically indicated following the guidelines outlined in the Risk Management Documentation Form. For patients scoring in the moderate or high-risk categories, a follow-up contact will be made with the parent/guardian and/or outpatient provider within 48 hours of the study call to assess follow-through with risk management recommendations provided by the study clinician. Participants will be informed that information they input to the app is not monitored for purposes of risk assessment.

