1.1 STUDY OBJECTIVES

1.1.1 PRIMARY OBJECTIVE

The primary objective of this study is to collect descriptive data to support feasibility, acceptability, safety, and potential for effectiveness.

- The potential for effectiveness is determined by examining participants' pre-test and post-test scores for SI and depression.
- The study will also collect data to guide refinements to the product and the workflow for product use.
- Participants will complete 12 sessions over approximately 12 weeks.
- Participants will complete assessments at baseline and weeks 1, 4, 8, and 12.
- Acceptability is determined from rates of session completion, rolling retention rate (percentage of participants who use the app on or after a set timeframe), and the system usability scale (SUS; Bangor et al., 2008), which indicates the extent to which participants found Oui's app usable.
- We will also conduct semi-structured user-feedback interviews.

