6.1.2 COLUMBIA-SUICIDE SEVERITY RATING SCALE (C-SSRS)

The C-SSRS is a rater-based interview to assess the severity and intensity of suicidal ideation and behaviors. Results will be presented for each question and within each of four constructs using counts and percentages over time: at week 4, week 8, and week 12.

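### SAP 6.1.2 leaves the week 1 C-SSRS form out of its tables, although week 1 is an SAP visit and the protocol collects the form there

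*SAP*

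**What the plan says.** SAP 6.1.2 plans C-SSRS results by item and by construct, "using counts and percentages over time: at week 4, week 8, and week 12". The SAP text contains no other C-SSRS analysis and gives no reason for this choice of visits.

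The SAP's own schedule, in 1.1.1, is wider: "Participants will complete assessments at baseline and weeks 1, 4, 8, and 12". It lists assessments in general and does not say which instrument is used at which visit.

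The protocol does say. The Timeline table has a row for "Columbia Suicide Severity Rating Scale (C-SSRS) – since last contact", marked at weeks 1, 4, 8, 12 and 16; the lifetime form is marked at week 0 only. The Risk Management section also lists week 1 among the interviews at which suicidality is assessed. Protocol B.2.5 makes suicide attempts and other suicidal behaviours, measured by the C-SSRS, a secondary endpoint followed over time.

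The two documents differ on length. Protocol Specific Aim 2 states: "This will be done in a single-site, 16-week, single-group clinical trial". B.2.6 pays for week 16, and the Timeline includes it. The SAP schedule stops at week 12.

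**The concern.** A since-last-contact form records an interval, not a state on the day. Once the week 1 call has taken place, the week 4 form asks about the time after that call. An attempt, an aborted attempt or other suicidal behaviour reported at week 1 is therefore not picked up by the week 4 form. If the SAP is followed as written, it has no place in any C-SSRS table.

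What is at stake is the completeness of a named secondary endpoint in the early post-discharge period. The protocol's Specific Aims and section A.2 single out that period: about half of suicide deaths in the year after psychiatric hospitalization are said to fall in the first month. That statement concerns deaths and gives no share for week 1. It shows why the interval is relevant, but it does not predict an event count here.

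**Working it through.** There is no planned figure to reproduce: the study is descriptive and the point rests on no power or alpha value. The check compares visit lists and counts forms.

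**Inputs**
- C-SSRS table visits (SAP 6.1.2): 4, 8, 12.
- SAP assessment visits after baseline (SAP 1.1.1): 1, 4, 8, 12.
- Visits with the since-last-contact form (protocol Timeline): 1, 4, 8, 12, 16.
- Participants (SAP section 2): 20.
- Assumption: every scheduled call is completed.

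**Step 1: visits not tabulated**
- SAP visits minus table visits: {1, 4, 8, 12} − {4, 8, 12} = {1}.
- Protocol visits minus table visits: {1, 4, 8, 12, 16} − {4, 8, 12} = {1, 16}.

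**Step 2: nominal interval covered by each form (gap to the previous visit)**

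| Visit week | 1 | 4 | 8 | 12 | 16 |
|---|---|---|---|---|---|
| Weeks covered | 1 | 3 | 4 | 4 | 4 |
| In the SAP C-SSRS table | no | yes | yes | yes | no |

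The table covers 3 + 4 + 4 = 11 of the SAP's 12 weeks (91.7%). The missing week is 1/12 = 8.3% of that schedule.

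**Step 3: forms, using the SAP's visits and the protocol's placement of the form**
- Scheduled: 20 × 4 = 80.
- Tabulated: 20 × 3 = 60.
- Not tabulated: 80 − 60 = 20, and 20/80 = 25%.

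**Step 4: only if the protocol's 16-week schedule governs**
- Scheduled: 20 × 5 = 100; not tabulated: 100 − 60 = 40 (40%).
- Weeks not covered: 1 + 4 = 5 of 16 (31%).
- Adding week 1 alone would bring coverage to 12 of 16 weeks (75%).

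**Step 5: how firm the interval is**

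The one-week length is nominal. The protocol says "Week 0 is the study baseline assessment, which occurs while the participant is housed in an inpatient treatment facility", and a Timeline footnote adds: "Visit 0 may take place over multiple sessions". B.2.6 counts week 1 as a post-discharge assessment. The documents do not fix the time from the baseline C-SSRS to the week 1 call, so no more exact share of follow-up time can be calculated.

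**Step 6: a missed week 1 call**

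If the week 1 call is missed, the last contact is earlier and the week 4 form reaches back over the gap. The loss therefore applies only to completed week 1 calls.

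**The case against.** **The SAP never places a C-SSRS form at week 1.** This is correct. SAP 1.1.1 lists visits only; the placement comes from the protocol. The 80-form count combines the two documents and should be labelled so. The omission stands, because the protocol is explicit that the form is collected then.

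**The choice may be deliberate.** SAP 6.1.1 uses the same three weeks for the System Usability Scale, so a reporting convention is plausible. For a usability score, a skipped visit costs one reading. For an interval form, it costs the interval. If the choice is deliberate, the SAP should give the reason.

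**The events are reported elsewhere.** This stands in part. Adverse events are assessed at week 1, and SAP 5.1 and 5.2 count participants and events. A reader might infer that week 1 events vanish from the report; the documents do not support that. However, those tables use MedDRA terms, and under B.2.9 adverse events are elicited by two general questions on physical and mental health. What is lost is the C-SSRS classification.

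**Per-visit tables are a legitimate display in a descriptive study.** They are. A reader might infer that the planned percentages are biased, or too low by 5 points (1/20) for each participant affected. Neither follows: behaviour reported only at week 1 does not belong in the week 4, 8 or 12 columns, and 6.1.2 plans no cumulative percentage from which it could be missing.

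**Week 16 is not a choice made in 6.1.2.** This is right. A reader might take the 40 forms and 31% in Step 4 as the size of the 6.1.2 omission. They are not: week 16 is absent from the SAP's whole schedule, so they depend on a conflict that must be settled first.

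**Conclusion.** The point holds and is minor. SAP 6.1.2, followed exactly, leaves the week 1 C-SSRS forms out of the only planned C-SSRS presentation. Behaviour reported at a completed week 1 call is then not shown by C-SSRS category.

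The size is 20 of 80 post-baseline forms (25%), nominally the first of 12 weeks. This assumes 20 participants, all calls completed, and the SAP's visits combined with the protocol's form placement. It is a count of forms, not an estimate of missed events. Sample size and inference are not affected.

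Two schedule conflicts lie next to this point but are separate from it. The protocol has a week 16 visit and the SAP ends at week 12. Within the protocol, the Risk Management list omits week 12 while the Timeline has the C-SSRS at week 12.

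**What to change.** **SAP 6.1.2:** add week 1, so that every post-baseline C-SSRS visit collected is tabulated, with the number of completed forms at that visit as the denominator.

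**Optional:** add one row giving the number of participants with any post-baseline suicidal behaviour, by C-SSRS category, over participants with at least one post-baseline form. Per-visit counts cannot be summed to this number, because one participant may report behaviour at several visits. The denominator should be stated in 6.1.2 itself, since the SAP text names the safety population only for adverse events.

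**Separately:** reconcile the SAP's 12-week schedule with the protocol's week 16 visit, and the Risk Management visit list with the Timeline on week 12. If week 16 is kept, tabulate it as well.

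**Cost:** a wording change in the SAP, one extra column and, if used, one row. A week 16 column follows only if that visit is kept. The forms are already scheduled, so no new data collection is needed.

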7 REPORTING CONVENTIONS

All reporting will meet the standards of SOP-68 AS Data Analysis Reporting and SOP-83 AS Programming Standards.

